### **6.13 Radiology Assessments**

After consent but before randomisation, patients who have not been investigated for coronary artery disease will have a screening CT coronary angiogram to confirm their eligibility for the study. We estimate that half of these patients will not have coronary artery disease, they will exit the study and not be randomised. The other half will have coronary disease and will then be randomised.

Of the randomised population, all will have a coronary angiogram, and half will have a percutaneous coronary intervention procedure. This includes patients who have had a prior angiogram or have had a CT coronary angiogram. All procedures will be performed as per clinical standards of care and no new scanning sequences will be used.

The study does not involve radioactive substances or radiotherapy and will be reviewed via the HRA-managed radiation assurance route.

## **7 LABORATORIES**

### **7.1 Central/Local Laboratories**

Blood samples will be collected using standard techniques and analysed in NHS hospital laboratories for full blood count, renal function, troponin and NT-pro-BNP. No tissues will be collected.

### **7.2 Sample Collection**

A total of 5ml of blood will be collected for full blood counts and 5ml for renal function, troponin and NT-pro-BNP. These samples will be taken for research purposes, except where they are measured clinically in which case tests will not be repeated. No samples will be stored. Results will be transcribed into the eCRF from clinical systems. Samples will be processed, stored and disposed in accordance with the information supplied in the participant consent forms and information sheets, as well as all applicable legal and regulatory requirements, including the Human Tissue Act 2004 and any amendments thereafter.

### **7.3 Sample Analysis Procedures**

Samples will be analysed using standard analysis techniques used for clinical samples in NHS laboratories. All tests are CE marked, considered standard for diagnostic purposes and used for their intended purposes.

## 8 END OF STUDY DEFINITION

The study will end when the final follow-up visit has been completed, all data entered, queries resolved, and the database locked.

## 9 ASSESSMENT OF SAFETY

### 9.1 Definition

**Unexpected** events that have not been defined as an outcome (see section 5.2) should be reported as either a serious adverse event (SAE) or non-serious adverse event (NSAE) depending on their severity.

### 9.2 Unexpected Serious Adverse Events

A SAE is defined as any untoward medical occurrence(s) that is life threatening, results in death, in-patient hospitalisation or prolongation of existing hospitalisation, persistent or significant disability/incapacity congenital anomaly or birth defect. Unexpected SAEs should be reported to the Clinical Trials Unit (CTU) within 7 days of the site becoming aware of the event. The report should include an assessment of causality by the Principal Investigator at each site. The Chief Investigator will be responsible for the prompt notification of findings that could adversely affect the health of patients or impact on the conduct of the trial.

### 9.3 Unexpected Non-Serious Adverse Events

Unexpected NSAEs should be evaluated by the Principal Investigator. This should include an assessment of causality and intensity and reports made within 14 days. The CTU will keep detailed records of all unexpected adverse events reported. Reports will be reviewed by the Chief Investigator to consider intensity, causality and expectedness.

### 9.4 Reporting Unexpected Adverse Events

Investigators will make their reports of all unexpected adverse events, whether serious or not, to the CTU at the London School of Hygiene & Tropical Medicine.

#### 9.4.1 Assessment of Intensity

Mild: The patient is aware of the event or symptom, but the event or symptom is easily tolerated.

Moderate: The patient experiences sufficient discomfort to interfere with or reduce their usual level of activity.

Severe: Significant impairment of functioning; the patient is unable to carry out usual activities and/or the patient's life is at risk from the event.

#### 9.4.2 Assessment of Causality

Probable: A causal relationship is clinically / biologically highly plausible and there is a plausible time sequence between onset of the adverse event and the PCI procedure.

Possible: A causal relationship is clinically / biologically plausible and there is a plausible time sequence between onset of the adverse event and the PCI procedure.

Unlikely: A causal relationship is improbable, and another documented cause of the adverse event is most plausible.

Unrelated: A causal relationship can definitely be excluded and another documented cause of the adverse event is most plausible.

### 9.5 Ethics Safety Reporting

The Sponsor, the Research Ethics Committee (REC) and the Data Monitoring Committee will be notified by the CTU when reported SAEs have been classified by the Chief Investigator as **both** unexpected and given a causality classification of either probable or possible.

Reports of **related** and **unexpected** SAEs will be submitted to the main REC within 15 days of the Chief Investigator becoming aware of the event, using the NHS HRA (non-CTIMP) template. The form should be completed in typescript and signed by the Chief Investigator. The main REC will acknowledge receipt of safety reports within 30 days.

A copy of the SAE notification and acknowledgement receipt should be sent to [[contact]](mailto:[contact]) and stored in the TMF/Site file. Appendices 3 and 4 contain a flowchart and further details of the process for reporting of serious and non-serious adverse events.

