#### **10.4 Data Monitoring Committee**

To ensure the safe conduct of the trial and respond to any safety concerns arising, a Data Monitoring Committee (DMC) will be convened. The DMC will comprise an independent chair, independent statistician and two further independent members who are practicing clinicians. The committee will meet prior to recruitment of the first patient and then at a frequency decided by the committee, with no more than one year permitted to elapse between meetings. A full report of the trial progress will be provided to the DMC by the unblinded statistician prior to each meeting. DMC meetings will involve an open session attended by members of the TMG, followed by a closed session for discussion of unblinded data. The DMC chair will provide a report to the TSC chair after the meeting has concluded. The activities of the DMC will be governed by a charter which will be signed by all members and circulated prior to recruitment of the first participant.

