### SAE Reporting Flow Diagram- Non CTIMPs.

#### APPENDIX 4: SAFETY REPORTING IN NON-CTIMP RESEARCH

	Who	When	How	To Whom
SAE (related and unexpected)	Chief Investigator	Report to Sponsor within 24 hours of learning of the event.  Report to the MREC within 15 days of learning of the event.	SAE Report form for Non-CTIMPs, available from NRES website.	Sponsor and MREC.
Urgent Safety Measures	Chief Investigator	Contact the Sponsor and MREC Immediately.  Within 3 days.	By phone.  Substantial amendment form giving notice in writing setting out the reasons for the urgent safety measures and the plan for future action.	Main REC and Sponsor.  Main REC with a copy also sent to the Sponsor. The MREC will acknowledge this within 30 days of receipt.
Progress Reports	Chief Investigator	Annually (starting 12 months after the date of favourable opinion).	Annual Progress Report Form (non-CTIMPs) available from the NRES website.	Main REC with a copy to be sent to the Sponsor.
Declaration of the conclusion or early termination of the study	Chief Investigator	Within 90 days (conclusion).  Within 15 days (early termination).  The end of study should be defined in the protocol.	End of Study Declaration form available from the NRES website.	Main REC with a copy to be sent to the Sponsor.
Summary of final Report	Chief Investigator	Within one year of conclusion of the Research.	No Standard Format However, the following Information should be included: Where the study has met its objectives, the main findings and arrangements for publication or dissemination including feedback to participants.	Main REC with a copy to be sent to the Sponsor.

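### Section 9.5 ties expedited SAE notice to the Chief Investigator's causality rating and gives the site's required rating no role when the two differ

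*Protocol*

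**What the plan says.** Reporting of an unexpected SAE runs in steps.

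- **Site report (9.2).** "Unexpected SAEs should be reported to the Clinical Trials Unit (CTU) within 7 days of the site becoming aware of the event". On its content: "The report should include an assessment of causality by the Principal Investigator at each site".
- **Central review (9.3).** "Reports will be reviewed by the Chief Investigator to consider intensity, causality and expectedness". The sentence stands under the heading for non-serious events, but it follows a statement about CTU records of all reported unexpected adverse events.
- **Notice by the CTU (9.5, first paragraph).** The Sponsor, the REC and the DMC are told "when reported SAEs have been classified by the Chief Investigator as" both "unexpected and given a causality classification of either probable or possible".
- **REC deadline (9.5, second paragraph).** Related and unexpected "SAEs will be submitted to the main REC within 15 days of the Chief Investigator becoming aware of the event".
- **Sponsor deadline (Appendix 4).** For the same class of event, the Chief Investigator's task is: "Report to Sponsor within 24 hours of learning of the event".

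Apart from this channel, section 10.4 gives the DMC a periodic view: "A full report of the trial progress will be provided to the DMC by the unblinded statistician prior to each meeting". The committee sets its own meeting frequency, with no gap longer than one year.

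**The concern.** Two causality ratings are planned for a serious event, one at the site and one by the Chief Investigator. The expedited trigger names only the second, and nothing readable in the protocol says what follows when the Chief Investigator's rating is the lower one.

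Differing ratings are foreseeable. In section 9.4.2 the probable and possible categories are both framed around the PCI procedure. Participants may also undergo a placebo procedure, deep conscious sedation and up to six months of clopidogrel or matching placebo (sections 6.5.2, 6.5.4.2 and 6.6). Two careful raters could apply that wording differently to an event linked to sedation or tablets.

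What is at stake is the timing of independent review. The Chief Investigator sits on the Trial Management Group and attends the Trial Steering Committee as a member (sections 10.1 and 10.2). The DMC is the independent body charged with safety. If the site's judgement cannot trigger notice, the DMC's view of such an event depends on when it next meets.

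**Working it through.** No figure in the protocol bears on this point, so the check is a comparison of the sections.

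**Step 1: who rates, and which rating triggers.** The site Principal Investigator rates causality in the report (9.2). The Chief Investigator's classification is the condition for CTU notice (9.5). For an SAE that the Chief Investigator accepts as unexpected, the first paragraph of 9.5 gives:

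| Site rating | Chief Investigator rating | Expedited notice required? |
|---|---|---|
| Probable or possible | Probable or possible | Yes |
| Unlikely or unrelated | Probable or possible | Yes |
| Probable or possible | Unlikely or unrelated | No |
| Unlikely or unrelated | Unlikely or unrelated | No |

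The answer follows the second column throughout; the first column never changes it. The third row is the gap.

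**Step 2: do other sections close the third row?** The second paragraph of 9.5 and Appendix 4 speak of related and unexpected SAEs without naming a rater. They neither give the site rating force nor deny it. Their clocks start when the Chief Investigator learns of the event, while the first paragraph of 9.5 waits for a completed classification, so the starting points also differ.

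**Step 3: how much traffic passes through this channel?** Section 5.2 lists outcomes that need no separate SAE report, and section 9.1 limits SAE reporting to unexpected events outside that list. The list includes death from any cause, myocardial infarction, stroke, hospital stays of at least 24 hours, new atrial fibrillation, bleeding, vascular complications, acute renal failure and repeat revascularisation. Set against the SAE definition in 9.2, this leaves mainly life-threatening or disabling events outside the list, admissions shorter than 24 hours, and prolongation of an existing stay.

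**Step 4: what remains for a third-row event?** The CTU keeps a record of it (9.3). The DMC receives a full progress report before each meeting (10.4). The REC, with a copy to the Sponsor, receives an annual progress report (Appendix 4). None of these reports has itemised contents, so they make later sight of the event likely but do not guarantee it. The longest permitted gap between DMC meetings is one year.

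**The case against.** The strongest reply is that 9.2 and 9.5 do not conflict. The site assesses, then the Chief Investigator classifies, and both steps can be followed as written. Central review of causality is a legitimate design, and nothing in the protocol requires that either rater alone should trigger a report. The first paragraph of 9.5 is also loosely built: it does not say outright who gives the causality classification, and a reader could take it to be the site's. The Appendix 3 flow diagram, to which 9.5 refers, could not be read for this point and may settle how differing ratings are handled.

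Most of this stands as a limit on the point. It does not remove it: the more natural reading of 9.5 is that the Chief Investigator's rating decides, and the text should not need a diagram to correct it.

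A reader might go further and infer that the Chief Investigator holds a veto, or that the Sponsor, the REC and the DMC would never be told. The documents support neither. No section grants a power to overrule the site; that is an inference from silence on disagreement. The CTU records, the DMC's pre-meeting reports and the annual reports contradict never. Nor are related-SAE notices the DMC's only assured information between meetings, since emergency unblinding is also reported to it (6.8.4).

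**Conclusion.** The point holds in a narrow form. As 9.5 is worded, expedited notice to the Sponsor, the REC and the DMC depends on the Chief Investigator's classification, and a higher site rating does not trigger it. The consequence is a possible loss or delay of expedited notice. For the DMC the wait could last until its next periodic report, at most one year between meetings and less if it chooses to meet more often.

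The conclusion rests on three conditions: the plain reading of the first paragraph of 9.5, an event that is unexpected and not a section 5.2 outcome, and an Appendix 3 diagram that does not already resolve disagreement. The protocol gives neither a count of such events nor a rate of disagreement, so no magnitude is quoted. It is a worthwhile clarification and does not threaten the trial's primary conclusions.

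**What to change.** State in 9.5 that the CTU notifies the Sponsor, the REC and the DMC when either the site investigator or the Chief Investigator rates an unexpected SAE as probable or possible, and that the report shows both ratings. Align Appendices 3 and 4 with that rule so that all three places name the same trigger.

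The cost is about one sentence in 9.5, matching wording in the appendices, and a few more expedited reports. The Chief Investigator's assessment is kept and stays visible beside the site's; it simply no longer decides alone whether notice goes out.

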## 10 TRIAL ORGANISATION

### 10.1 Trial Management Group

The trial will be managed by the accredited London School of Hygiene & Tropical Medicine CTU (UK Clinical Research Collaboration number 44). The Trial Management Group (TMG) comprising the Chief Investigator, patient Co-Applicant, trial manager and senior manager will meet at least once per month and more frequently as needed to review trial progress, recruitment and manage any issues arising.

### 10.2 Trial Steering Committee

The trial will be overseen by a Trial Steering Committee (TSC). The committee will comprise an independent chair and five other independent members including two representatives of patients and the public, the Chief Investigator and Trial Statistician. TSC meetings will be open to members of the public and interested parties as observers. The committee will meet prior to recruitment of the first participant and then at a frequency decided by the committee, with no more than one year permitted to elapse between meetings. The TSC will oversee the conduct of the trial, including decisions about stopping or continuing the trial, in co-ordination with the Sponsor and funder. The activities of the TSC will be governed by a charter which will be signed by all members and circulated prior to recruitment of the first participant.

### 10.3 Patient Advisory Committee

A Patient Advisory Committee (PAC) will be set up for the trial and consist of at least six members with lived experience of heart failure, coronary artery disease and/or involvement in interventional cardiology trials. The group will meet approximately every three months to review progress and trial matters. They will assist in the drafting and reviewing of all participant materials. Two members of the PAC will also sit as independent members of the TSC with oversight of the whole study. Activities of the PAC will be guided by a terms of reference.

#### **10.4 Data Monitoring Committee**

To ensure the safe conduct of the trial and respond to any safety concerns arising, a Data Monitoring Committee (DMC) will be convened. The DMC will comprise an independent chair, independent statistician and two further independent members who are practicing clinicians. The committee will meet prior to recruitment of the first patient and then at a frequency decided by the committee, with no more than one year permitted to elapse between meetings. A full report of the trial progress will be provided to the DMC by the unblinded statistician prior to each meeting. DMC meetings will involve an open session attended by members of the TMG, followed by a closed session for discussion of unblinded data. The DMC chair will provide a report to the TSC chair after the meeting has concluded. The activities of the DMC will be governed by a charter which will be signed by all members and circulated prior to recruitment of the first participant.

### **11 ETHICS & HRA APPROVALS**

The study requires regulatory approval from the following bodies (NHS REC London - Riverside Favourable Opinion and HRA Approval, REF 25/LO/0277).

#### **11.1 Required conditions before recruitment can start at trial sites**

Before any site can enrol patients into the study, the Chief Investigator (CI)/Principal Investigator or designee will ensure that the appropriate regulatory approvals have been issued, and NHS Confirmations of Capacity and Capability and Sponsor green lights are in place.

#### **11.2 Amendments**

For any amendments to the study, the CI or designee, in agreement with the Sponsor, will submit information to the appropriate body in order for them to issue approval for the amendment. The CI or designee will work with sites (R&D departments as well as the study delivery team) to confirm ongoing Capacity and Capability for the study.

#### **11.3 Correspondence**

All correspondence with the Sponsor, REC and HRA will be retained. The CI will notify the Sponsor and REC of the end of the study.

## 12 COMPLIANCE AND WITHDRAWAL

### 12.1 Participant compliance

Participants will be encouraged to complete all study procedures and assessments at the appropriate timepoints or at the closest practicable timepoint. Where a participant has not attended a follow-up appointment, site teams will make every effort to contact them using all available telephone numbers and email. If a participant is uncontactable after these initial efforts, research team members will send a letter to the participant requesting them to contact the team. The clinical team and patient's general practitioner will also be contacted to ascertain if there is a reason they have not been able to contact the participant and attempt to facilitate contact.

If participants are unable to be contacted despite persistent efforts from the research team, they will be considered lost to follow-up. Local teams will use patient health records and searches of national registries will be used to confirm vital status. Completeness of follow-up for the primary endpoint will be determined from the trial eCRF and reported. As the trial allocation is to an initial intervention, details of ongoing compliance with treatment are not relevant and will not be recorded.

### 12.2 Withdrawal / dropout of participants

Participants are free to withdraw from the trial at any time and without having to provide a reason. Their clinical care will not be disadvantaged by their withdrawal from the study.

At the time of withdrawal, participants will be offered three options for withdrawal:

1. Participants may withdraw from active follow-up and further communication but allow the trial team to continue to access their medical records and any relevant hospital data that are recorded as part of routine standard of care; i.e., blood tests, echocardiograms and available measures of health status (e.g. NYHA class and CCS class).
2. Participants can withdraw from the study but permit data and samples obtained up until the point of withdrawal to be retained for use in the study analysis. No further data or samples would be collected after withdrawal.
3. Participants can withdraw completely from the study and withdraw the data and samples collected up until the point of withdrawal. The data and samples already collected would not be used in the final study analysis. (Any limits to this type of withdrawal where, for example analysis of their data or samples has already been integrated into interim results, should be explained in the participant information sheet).

In situations where the participant withdraws but does not specifically indicate a preference, data and samples obtained up until the point of withdrawal will be retained for use in the study analysis. No further data or samples would be collected.

#### 12.2.1 Recording participant withdrawal in the eCRF

Details of the participant withdrawal will be completed by the CTU team via the Participant Withdrawal form in the eCRF, including reasons for withdrawal where given. Immediately prior to withdrawal, participants will be asked if they consent to completing a final follow-up for completion of the primary outcome data.

#### 12.2.2 Withdrawal due to an adverse event

If the participant is withdrawn due to an adverse event, the PI will arrange for follow-up visits or telephone calls until the adverse event has resolved or stabilised.

### **12.3 Protocol Compliance**

Every effort should be made to adhere to the protocol. A protocol deviation is usually an unintended departure from the expected conduct of the study protocol/WPDs, which does not need to be reported to the Sponsor. The CI will monitor protocol deviations and list them in a deviation log and include a file note in the TMF/sites file where applicable.

Significant deviations to the protocol or deviations which are found to frequently recur are not acceptable and need to be assessed by the CI to see if an amendment to the protocol is required. These will require reporting to the Sponsor and action taken through Corrective and Preventative Actions (CAPA).

A 'serious breach' is defined as a breach likely to effect to a significant degree:

- The safety or physical or mental integrity of the participants of the trial;
- The scientific value of the trial.

The CI and Sponsor must be notified immediately of a serious breach. The breach must be reported to the REC with the Sponsor in copy within **7 calendar days** of the breach being confirmed as serious.

